I have read this protocol and agree that it contains all the necessary details for performing the study in accordance with the Declaration of Helsinki and the International Conference on Harmonization (ICH) for Good Clinical Practice (GCP).

I will provide copies of the protocol and of the clinical and preclinical information on the investigational product, which was furnished to me by the Sponsor (Spectrum Pharmaceuticals, Inc.), to all members of the study team responsible to me who participate in the study. I will discuss this material with them to assure that they are fully informed regarding the study drug and the conduct of the study.

I will perform the study according to specifications outlined in the protocol and agree to implement protocol requirements only after the protocol and patient information/Informed Consent form have been approved by the Institutional Review Board/Ethics Committee (IRB/EC). I will submit any protocol modifications (amendments) and/or any Informed Consent form modifications to the IRB/EC, and approval will be obtained before any modifications are implemented.

I understand that the information presented in this study protocol is confidential, and I hereby assure that no information based on the conduct of the study will be released without prior consent from Spectrum Pharmaceuticals, Inc., unless this requirement is superseded by a regulatory authority (eg, FDA).

Investigator Name (PLEASE PRINT):

Signature: _____ **Date** _____

SYNOPSIS

Title of Study: A Randomized, Multicenter, Two-Arm, Single-Dose, Double-Blind, Placebo- C ONTrolled Phase 3 Study of Intravesical Q apzola™ (Apaziqone) as a Chemotherapy Adjuvant to Trans U rethral Resection of Bladder Tumors in Patients with Low- to Intermediat E - R isk Non-Muscle Invasive Bladder Cancer (C ON Q UER)	
Name of Sponsor: Spectrum Pharmaceuticals, Inc.	
Name of Investigational Product: Qapzola™ (apaziqone)	
Planned Number of Patients: Approximately 500 patients will be enrolled to obtain 425 target disease patients in two treatment arms.	
Study Centers: Approximately 70 study centers globally.	
Duration of Study: Approximately 5 years (2.5 years accrual + 2.5 years follow-up)	Clinical Phase: 3
OBJECTIVES: Primary Objective(s) 
To evaluate the Time to Recurrence in patients with low- to intermediate-risk non-muscle invasive bladder cancer (NMIBC) who receive either 8 mg Qapzola or placebo post transurethral resection of bladder tumor (TURBT). Secondary Objectives 
To evaluate the following in patients with low- to intermediate-risk NMIBC who receive either 8 mg Qapzola or placebo post-TURBT:
 
2-Year Recurrence RateExtent of Disease at Recurrence (number, and location of tumors)Time to Disease Progression (based on the tumor stage)Safety	
STUDY DESIGN AND TREATMENT PLAN: 
This is a randomized, multicenter, two-arm, double-blind, placebo-controlled study of Qapzola in patients with low- to intermediate-risk NMIBC, assessed according to the 2016 American Urology Association (AUA) Guidelines. Specifically, only patients with tumor characteristics in bold text in the low- to intermediate-risk columns of the table below will be included in the study.
	

2016 American Urological Association Stratification for Non-Muscle Invasive Bladder Cancer		
Low Risk	Intermediate Risk	High Risk

 • Low grade solitary Ta ≤ 3cm* • PUNLMP* 	
 • Recurrence within 1 year, low-grade Ta* • Solitary low-grade Ta >3 cm* • Low-grade Ta, multifocal* • High-grade Ta, ≤ 3 cm (solitary tumor)* • Low-grade T1 	
 • High grade T1 • Any recurrent, high grade Ta • High grade Ta, >3 cm (or multifocal) • Any CIS • Any BCG failure in high-grade patient • Any variant histology • Any lymphovascular invasion • Any high-grade prostatic urethral involvement

* - histology for evaluable target population

In addition to other Screening assessments, patients will undergo an assessment of urothelial carcinoma of the bladder via cystoscopy for clinically apparent tumor of Ta histology, including PUNLMP. The qualifying cystoscopy may be performed up to 45 days prior to signing the informed consent.

Eligible patients will be randomized in a 2:1 ratio to either:

- **Arm 1:** One dose of 8 mg Qapzola
- **Arm 2:** One dose of placebo

Once approved for randomization, patients will undergo TURBT on Day 1 and the study drug instillation will occur at 60 ± 30 minutes post-TURBT and will be retained for 60 minutes (± 5 minutes) in the bladder. All histology specimens will be reviewed by a local pathology laboratory and all clinical treatment decisions will be based on the local pathology review. Patient target disease will be confirmed and efficacy analyses will be performed based on the pathology results. The target study population is low- to intermediate-risk patients who have Ta histology, including PUNLMP, as confirmed by a pathology laboratory. Patients whose tumor histology does not meet the criteria for eligibility, as confirmed by pathology (Non-Target Population), will be followed up for safety on Day 35 (± 5 days) (Safety Follow-up Visit) and will be discontinued from the study. If the pathology results are delayed beyond 35 days, the Safety Follow-up Visit will be conducted when the results are available for these patients.

Patients who have pathology confirmed target histology will not receive additional medications to treat NMIBC during the follow-up while on study. All target disease patients will be followed until either a confirmed tumor recurrence, additional bladder cancer treatments, or until the End-of-Study, whichever occurs first.

The primary analysis will be conducted once the required number of recurrence events are observed as detailed in the Statistical Methods below. A recurrence is defined as any pathologically confirmed disease of \geq Ta histology or CIS post-treatment. The number of events needed to perform the final primary endpoint analysis was estimated based on the recurrence rate at 24 months from previous studies. The follow-up schedule is below:

- Cystoscopic examination and urine cytology every 3 months (± 30 days) (calculated from date of TURBT) for 2 years for tumor recurrence and progression and then every 6 months (± 60 days) until either a confirmed tumor recurrence or the End-of-Study, whichever occurs first.
- If at any time during the study there is a histologically confirmed tumor recurrence, the patient will be discontinued from the study at that time and may then be treated per the Investigator's standard of care.

The study will end (End-of-Study) when the required number of events for the primary endpoint analysis are accrued.

Duration of Study: The duration of the study for each patient will be as follows:

- **Screening Period:** up to 30-days
- **Treatment:** Day 1
- **Safety Follow-up:** Day 35 (± 5 days) (non-Target Population) or Month 3 Follow-up Visit (Target Population)
- **Follow-up Period:** No follow-up in non-Target Population. Until either a confirmed tumor recurrence or the End-of-Study, whichever occurs first in Target Population.

Patient Replacement Strategy: If a patient is confirmed to have non-target disease after TURBT, the patient will not be considered evaluable for analysis. Enrollment will continue until the study reaches the required number of target-disease evaluable patients.

INCLUSION & EXCLUSION CRITERIA:

Inclusion Criteria:

1. Patient must have a clinical diagnosis of low- to intermediate-risk non-muscle invasive bladder cancer according to the 2016 American Urological Association (AUA) Guidelines
2. Patient must be willing to give written informed consent and must be able to adhere to dosing and visit schedules, and meet all study requirements.
3. Patient is at least 18 years of age and <90 years of age at the time Informed Consent is signed.
4. Patient must be willing to practice two forms of contraception, one of which must be a barrier method, from study entry until at least 35 days after study treatment. Patients surgically sterilized or who are postmenopausal for at least 1 year (defined as more than 12 months since last menses) do not require contraception.
5. Females of childbearing potential must have a negative pregnancy test within 30 days prior to randomization. Females who are postmenopausal for at least 1 year (defined as more than 12 months since last menses) or are surgically sterilized do not require this test.

Exclusion Criteria:

1. Patient has malignancy or life-threatening systemic disease or a history of advanced, serious, life-threatening malignancy/disease within the last 5 years, except very low-risk prostate cancer
2. Patient has used any investigational drugs, biologics (vaccines, antibodies), or devices within 30 days prior to study treatment or has plans to use any of these during the course of the study
3. Patient has received any pelvic radiotherapy (including external beam and/or brachytherapy).
4. Patient has a history of allergy to red color food dye or any other component of Qapzola, placebo, or their diluents
5. Patient has had a surgical procedure 4 weeks prior to TURBT or will have other surgical procedures performed at the time of TURBT or within 4 weeks after TURBT
6. Patient has any unstable or uncontrolled medical condition that would make it potentially unsafe to undergo TURBT including a previous stroke or myocardial infarction within 6 months
7. Patient has an active uncontrolled infection, including a urinary tract infection, underlying medical condition, or other serious illness that would impair the ability of the patient to receive study treatment or undergo study procedures
8. Patient has a bleeding disorder or a screening platelet count $<100 \times 10^9/L$, or requires continuous anticoagulation or bridging anticoagulation during the procedure
9. Patient has a hemoglobin value <10 g/dL at Screening
10. Patient has ever had confirmed extravesical urothelial disease (upper tract and urethral including prostatic urethral)
11. Patient with a history of previous bladder cancer:
 - High-Risk NMIBC as classified per the 2016 AUA Guidelines
 - Bladder cancer that was muscle invasive or positive for lymph node or distant metastasis

12. Patient has received any previous intravesical therapy for bladder cancer- chemotherapy, immunotherapy, or previous exposure to Qapzola in the last 3 years
13. Patient has a tumor in the bladder diverticulum
14. Patient has a history of interstitial cystitis
15. Patient is pregnant or breast-feeding

DOSE AND ROUTE OF ADMINISTRATION:

One dose of either 8 mg/50 mL Qapzola or volume and appearance matched placebo will be administered by intravesical administration into the bladder at 60 ± 30 minutes post TURBT (Day 1) via an indwelling 100% Silicone Foley catheter and will be retained in the bladder for 60 ± 5 minutes.

EFFICACY ASSESSMENTS:

Cystoscopic examination and urine cytology test every 3 months (± 30 days) (calculated from date of TURBT) for the first 2 years for tumor recurrence and progression and then every 6 months (± 60 days) until either a confirmed tumor recurrence or the End-of-Study, whichever occurs first. Pathology review will be performed by local laboratories on tissue/tumor specimens from cystoscopy or TURBT, whichever is conducted for the follow-up assessment.

Primary Endpoint:

- Time to Recurrence in patients with low- to intermediate-risk NMIBC who receive either 8 mg Qapzola or placebo following TURBT.

The primary analysis will be conducted once a total of 208 recurrence events have occurred in the study.

Secondary Endpoints:

1. 2-Year Recurrence Rate
2. Extent of Disease at Recurrence (number and location of tumors)
3. Time to Disease Progression (based on the tumor stage)
4. Safety

SAFETY ASSESSMENTS:

Safety will be assessed by reported/elicited adverse events (AEs), laboratory test assessments, and physical examinations.

Safety Endpoints

- All AEs
- Treatment-related adverse events
- Serious Adverse Events (SAEs)
- AEs leading to discontinuation
- AEs of special interest (\geq grade 3 dysuria and hematuria)
- Vital signs (body temperature, blood pressure and heart rate) and routine laboratory test parameters (complete blood count and blood chemistry)
- Deaths

Adverse Event and Serious Adverse Event Reporting:

From the time the study Informed Consent is signed through the day of study drug administration, only SAEs that are related to study procedures are to be recorded. For all non-Target population patients, all adverse events from the time of study drug administration until Day 35 (± 5 days) post-TURBT will be recorded. For Target population patients, all adverse events will be recorded from the time of study drug administration until the 3-month Follow-up Visit. Only deaths and AEs related to study procedures will be recorded for the remainder of the follow-up period.

Independent Data Monitoring Committee (IDMC)

The safety of the 8 mg/50 mL Qapzola dose will be evaluated by an IDMC for the first 30 patients treated in the study. Continuation of the study at this dose level will be determined based on the IDMC evaluation. The IDMC is also responsible for the review of the unblinded futility analysis.

STATISTICAL METHODS:

The primary analysis population is the Target Population, which will consist of all patients with confirmed low-to-intermediate-risk NMIBC. The stage and grade determination for the Target Population will come from the pathology review. Tumors will be graded using 2004 WHO/ISUP criteria.

The Safety Population includes all patients who have had a TURBT and have received treatment of study drug (Qapzola or placebo).

The enrolled patients will be randomized in a 2:1 ratio to either Qapzola or placebo. The primary endpoint is Time to Recurrence in the Target Population. The primary endpoint analysis involves a test of comparison: 8 mg Qapzola vs. placebo using 2-sided log-rank test at 5% level of significance.

The Time to Recurrence is defined as time from Day 1 Treatment to the date of the first histologically confirmed recurrence (using the date of corresponding cystoscopy) of the patient's bladder tumor. Patients without recurrence at the time of the primary analysis will be censored at the last available date of cystoscopy. Patients who died due to any cause before confirmed recurrence will be censored at the last available date of cystoscopy.

The following sensitivity analyses will be performed for the primary analysis.

1. Analysis of time to recurrence by excluding patients who miss 2 consecutive cystoscopies or lost to follow-up either prior to recurrence or prior to the date of the primary analysis – Completer analysis
2. Analysis of time to recurrence by excluding patients who miss 2 consecutive cystoscopies or lost to follow-up either prior to recurrence or prior to patient's follow-up duration of 24 months – Completer 24 Month analysis
3. Analysis of time to recurrence by considering patients with no recurrence who miss 2 consecutive cystoscopies or lost to follow-up prior to date of the primary analysis as recurred.

The primary analysis will be conducted using a hierarchical procedure of hypothesis testing at a 5% level of significance. The primary endpoint, Time to Recurrence, will be examined first, and if significant, the secondary endpoint, 2-Year Recurrence Rate, will be examined next, and if also significant, Extent of Disease at Recurrence, and Time to Disease Progression will then be examined in that order.

Approximately 500 patients will be enrolled and treated in this study. Accrual time is estimated as 24 months and follow-up time as approximately 24 months. For the sample size calculation, a hazard ratio (HR) of 0.65 is assumed for the improvement in Time to Recurrence in favor of Qapzola as compared to the placebo with a hazard rate of 0.3 in placebo arm. In a 2:1 randomization of Qapzola and placebo, sample sizes of 284 in APZ and 141 in PBO Target disease patients (total of 425) will provide 85% power. This sample size is estimated to provide a total of 208 recurrence events during the follow-up duration of at least 24 months. The primary analysis will be conducted once a total of 208 recurrence events are observed. The events will be monitored in a blinded fashion regardless of the treatment assignment to determine the timing of the primary analysis. All secondary endpoint analyses will be conducted at the time of the primary analysis.

Since the Target population is confirmed by the pathology review and this will be performed after patients are randomized and have undergone TURBT procedure, the study will account for misclassification in Target disease population. Accounting for 15% misclassification of randomized patients, the study will enroll approximately 500 patients. However, the study will continue to enroll patients until the required number of Target disease patients are accrued.

A futility analysis will be performed during the study conduct to determine the study continuation. The futility analysis will be conducted in the Target patients once 60 events are observed. The study will be stopped for futility if the calculated z-value from the log-rank test of HR is >1.0 . No adjustment for multiplicity of comparison will be made for futility analysis and the final analysis will be performed at 5% level of significance.

The interim analysis will also be used to determine if additional subjects should be recruited to ensure that enough events would be accumulated at approximately 2-year follow-up from drug instillation. Based on the expected events of 208 out of 425 subjects after 2-year follow-up, we anticipate that the first 123 subjects should have completed 2-year follow-up visits at the futility analysis when 60 events are observed. However, if lower

[figure not shown]
overall recurrence rate is observed, additional patients in the Target Population will be recruited in order to accrue required number of events.

The interim analysis will be performed by an Independent Data Monitoring Committee (IDMC) that will have access to the unblinded data. The study team will be blinded to the treatment allocation during the follow-up period.

All treatment-emergent adverse events will be graded according to National Cancer Institute Common Terminology Criteria for Adverse Events (NCI CTCAE) version 4.03, and grouped by the MedDRA System Organ Class and Preferred Term, and summarized by worst grade severity per patient.

Original Protocol: 22 Dec 2016

Study Flow Chart

Schedule of Study Assessments and Procedures

Assessments	Screening	Randomize/ Treatment	Safety Follow-up Visit ^a	Long-Term Post-TURBT Follow-up ^b									
	Day -30 to 1	Day 1	Day 35	Month								Every 6 Months	
				3 ^a	6	9	12	15	18	21	24		
	Visit 0	Visit 1	Visit 2	Visits 3-10								Visits 11+	
Informed Consent (IC)	x												
Urine cytology	x ^c			x	x	x	x	x	x	x	x	x	x
Cystoscopy	x ^c			x	x	x	x	x	x	x	x	x	x
Medical history	x												
Vital signs	x	x	x	x									
Weight and height	x												
Physical examination ^d	x		x	x									
Complete Blood Count	x	x ^e	x	x									
Chemistry	x	x ^e	x	x									
Pregnancy test	x												
Urine dip stick	x	x ^{e,f}	x	x	x	x	x	x	x	x	x	x	x
TURBT and Specimen Collection		x ^g											
Randomization		x											
Qapzola or Placebo instillation ^h		x											
Concomitant medications ⁱ	x	x	x	x	x	x	x	x	x	x	x	x	x
Adverse event assessment ^j	x	x	x	x	x	x	x	x	x	x	x	x	x

- a) Only patients who don't have pathology confirmed study-eligible NMIBC after TURBT, or patients who discontinue during follow-up, will return on Day 35 (±5 days) for the Safety Follow-up Visit. Patients in the Target Population will have the Safety Follow-up at the 3-month visit.
- b) Follow-up visits for patients with Ta histology are to be conducted every 3 months (±30 days) calculated from the date of TURBT for the first 2 years and then every 6 months (±60 days) until tumor recurrence or the End-of-Study, whichever occurs first.
- c) The qualifying cystoscopy and urine cytology may be performed up to 45 days prior to signing the informed consent.
- d) A complete physical examination will be performed at Screening and the Safety Follow-up Visit/Month 3 Follow-up Visit. At all other visits, a physical examination is only required as indicated.
- e) If the screening assessments for the physical examination, hematology, chemistry, urine dipstick were performed within 3 days (72 hours) prior to Day 1/TURBT, these assessments do not need to be repeated at the Day 1 Visit. If patient is on anticoagulation therapy or has bleeding disorder risk, PT/PTT test should be ordered at Screening per investigator discretion.
- f) Urine dipstick to be done just prior to study drug instillation (60 ± 30 minutes) once gross hematuria is resolved.
- g) Each tumor/lesion resected during TURBT should be submitted to the local pathology lab in a separate container, noting the location, to ensure that the tumor location, size, stage, and grade for each tumor/lesion, according to the 2004 WHO/ISUP grading system along with the presence/absence of muscle fiber in the lesion, is assessed.
- h) Instillation of study drug (Qapzola or placebo) is to be performed at 60 ± 30 minutes post-TURBT procedure on Day 1 and is to be retained in the bladder for 60 ± 5 minutes.
- i) During the Follow-up Period, only medications to treat NMIBC will be recorded for concomitant medications.
- j) All adverse events from the time of study drug administration until 35 days after the last dose of study treatment will be recorded. From the 3-month visit through the End-of-Study, only deaths and AEs related to study procedures will be recorded.

TABLE OF CONTENTS

TITLE PAGE	1
INVESTIGATOR SIGNATURE.....	2
SYNOPSIS.....	3
TABLE OF CONTENTS	11
List of Figures.....	14
LIST OF ABBREVIATIONS AND DEFINITIONS OF TERMS	15
1 INTRODUCTION AND BACKGROUND	17
1.1 Non-Muscle Invasive Bladder Cancer	17
1.2 Qapzola for Intravesical Instillation	17
1.3 Clinical Studies with Qapzola	18
1.3.1 Clinical Efficacy of Qapzola	18
1.3.1.1 2-Year Recurrence Rate	19
1.3.1.2 Time to Recurrence	19
1.3.1.3 Other Secondary Efficacy Parameters	21
1.3.1.4 Time to Instillation	21
1.3.2 Clinical Safety of Qapzola.....	22
1.4 Study Rationale.....	23
2 STUDY OBJECTIVES	26
2.1 Primary Objective(s)	26
2.2 Secondary Objectives.....	26
3 INVESTIGATIONAL PLAN	26
3.1 Study Design and Treatment Plan.....	26
3.2 Study Duration	27
4 PATIENT POPULATION.....	28
4.1 Inclusion Criteria	28
4.2 Exclusion Criteria	28
4.3 Patient Discontinuation/Withdrawal Criteria.....	29
5 STUDY PROCEDURES	29
5.1 Screening.....	30
5.2 Patient Assignment	31
5.3 Timing of Assessments and Procedures	31
5.3.1 Screening	31
5.3.2 Treatment Period: Visit 1 (Day 1).....	32

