Since there was only one instillation, there were no AEs that led to discontinuation of study drug instillation. Approximately 4% of patients discontinued from the studies due to AEs over the 2-year study period, with the incidence of these AEs being similar between studies and between treatment groups, and no individual AE occurring in more than 1% of patients. None of the AEs leading to discontinuation were assessed as related to study treatment by the Investigator.

Approximately 3% of patients had AEs that resulted in death, none of which the investigator assessed as related to study drug (Qapzola or placebo). There were no deaths reported in the immediate post TURBT instillation period (within 30 days).

Clinical laboratory assessments showed no clinically meaningful differences between patients receiving Qapzola and placebo in any hematologic, liver, kidney, or metabolic parameters and in a subgroup of patients in SPI-611 (n=191), there was no measurable effect on functional bladder capacity.

Data from the other six studies were supportive of the safety data in SPI-611 and SPI-612. Among the 245 patients in these studies, 139 received multiple instillations of Qapzola. The types of TEAEs in these patients were similar to those in SPI-611 and SPI-612, although the incidence of dysuria, hematuria, pollakiuria, and micturition urgency tended to be higher in

patients receiving multiple instillations of Qapzola (~15% to 45%) than single instillations (~3% to 15%). Treatment-related SAEs were experienced by three patients who received single instillations of Qapzola (pelvic pain, postoperative urinary retention, and hematuria) and four patients receiving multiple instillations of Qapzola (dysuria, hematuria and hemorrhage urinary tract, chemical cystitis, pollakiuria); all patients recovered. No patients in the supportive safety studies discontinued due to AEs and none died.

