5.4.5 Vital Sign Assessments

Temperature, blood pressure, and heart rate are to be recorded at Screening, at the Treatment Visit, and the Safety Follow-up/Month 3 Follow-up Visit.

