8.6.1 Safety Endpoints

- All AEs

- Related Adverse Events
- Serious Adverse Events (SAEs)
- AEs leading to drug discontinuation
- Vital signs (body temperature, blood pressure, and heart rate) and routine laboratory parameters (hematology, chemistry)
- Deaths

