Official Title: A Randomized, Multicenter, Two-Arm, Single-Dose, Double- Blind, Placebo-CONTROLLED Phase 3 Study of Intravesical Qapzola™ (Apaziquone) as a Chemotherapy Adjuvant to TransUrEthral Resection of Bladder Tumors in Patients with Low- to Intermediate-Risk Non-Muscle Invasive Bladder Cancer (CONQUER)

NCT Number: NCT03224182

Document Date: SAP Version 1.0: 30 May 2019

STATISTICAL ANALYSIS PLAN

Study: SPI-QAP-306

Title: A Randomized, Multicenter, Two-Arm, Single-Dose, Double-Blind, Placebo-CONTROLLED Phase 3 Study of Intravesical Qapzola™ (Apaziquone) as a Chemotherapy Adjuvant to TransUrEthral Resection of Bladder Tumors in Patients with Low- to Intermediate-Risk Non-Muscle Invasive Bladder Cancer (CONQUER)

Sponsor: Spectrum Pharmaceuticals, Inc.

Version: 1.0

Date: 30 May 2019

Author: [Redacted] 8/27/2020

[Redacted], PhD Date
[Redacted]

Approval: [Redacted] 8/27/2020

[Redacted], PhD Date
[Redacted]

Summary of Changes from protocol

The SAP is to accommodate the early termination of the study due to business reason. Important changes are summarized below.

1. All efficacy objectives are removed.
2. All efficacy endpoints are removed, including all corresponding analysis.
3. The following Analysis Populations are removed.
 - Target Population
 - Non-Target Population
 - Per-Protocol (PP) Population
4. Interim Analysis is removed.
5. Sensitivity analysis and subgroup analysis are removed.

TABLE OF CONTENTS

TABLE OF CONTENTS	3
1 INTRODUCTION	4
2 STUDY OBJECTIVES	4
2.1 Primary Objective.....	4
3 INVESTIGATIONAL PLAN	4
3.1 Study Population.....	4
3.2 Study Design	4
3.3 Study Duration	5
3.4 Study Endpoints.....	5
3.4.1 Efficacy Endpoints.....	5
3.4.2 Safety Endpoints.....	5
4 STATISTICAL CONSIDERATIONS.....	5
4.1 General Analysis Considerations.....	5
4.2 Sample Size	5
4.3 Randomization	6
4.4 Baseline Measurements	6
4.5 Handling of Missing Data.....	6
4.6 Analysis Population	7
4.7 Final Analysis	7
5 STUDY PATIENTS.....	7
5.1 Disposition of Patients	7
5.2 Pretreatment Characteristics.....	7
6 EFFICACY EVALUATION.....	7
7 SAFETY EVALUATION	7
7.1 Extent of Exposure.....	7
7.2 Concomitant Medications	7
7.3 Adverse Events	7
7.3.1 Treatment Emergent Adverse Events.....	7
7.3.2 Treatment-Related Adverse Events	8
7.3.3 Serious Adverse Events	8
7.3.4 Other Important Adverse Events.....	8
7.4 Clinical Laboratory Evaluations	8
8 REFERENCES	8

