3.4.2 Safety Endpoints

- All TEAEs
- Treatment related adverse events
- Serious Adverse Events (SAEs)
- TEAEs leading to drug discontinuation
- Routine laboratory test parameters (hematology, chemistry)
- Deaths

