7.3.1 Treatment Emergent Adverse Events

A TEAE is any AE that occurs from the first dose of study treatment until 35 days after the last dose of study drug administration. TEAEs will be graded according to National Cancer Institute

Common Terminology Criteria for Adverse Events (NCI CTCAE) version 4.03, and grouped by the MedDRA preferred term, and summarized by worst grade severity per patient by treatment arms.

The incidences of treatment emergent AEs will be presented by MedDRA SOC and PT with any grade and with Grade 3 or 4. Patients who experience more than one type of AE will be counted under each of the corresponding PT. Patients who experience different episodes of the same AE will be counted only once under the corresponding PT. Similarly, for determination of MedDRA SOC incidences, patients who experience multiple AEs under the same SOC will be counted only once for that SOC. Listing of all TEAEs will also be provided.

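### The safety-only SAP omits vital signs and the named count of grade 3 or higher dysuria and hematuria, and declares neither omission

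*Protocol*

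**What the plan says.** **Protocol synopsis, Safety Endpoints.** The list has seven bullets. One names AEs of special interest, at or above "grade 3 dysuria and hematuria". Another reads "Vital signs (body temperature, blood pressure and heart rate) and routine laboratory test parameters (complete blood count and blood chemistry".

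**Protocol Section 8.6.1.** The list has six bullets. It keeps "Vital signs (body temperature, blood pressure, and heart rate) and routine laboratory parameters (hematology, chemistry" and has no AESI line.

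**Protocol Section 5.4.5.** Vital signs are collected: "Temperature, blood pressure, and heart rate are to be recorded at Screening, at the Treatment Visit, and the Safety Follow-up/Month 3 Follow-up Visit".

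**SAP Section 3.4.2.** The list has six bullets. The combined bullet now reads "Routine laboratory test parameters (hematology, chemistry", so vital signs are gone, and there is no AESI bullet.

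**SAP Section 7.3.1.** This section keeps a general tabulation: "The incidences of treatment emergent AEs will be presented by MedDRA SOC and PT with any grade and with Grade 3 or 4". It also plans a worst-grade summary per patient by arm and a listing of all TEAEs. Section 7.3.4, on other important events, covers only death and discontinuation of study drug.

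**SAP Summary of Changes.** It opens with "Important changes are summarized below" and gives five items: efficacy objectives; efficacy endpoints and their analyses; three analysis populations; the interim analysis; and sensitivity and subgroup analyses. None concerns a safety endpoint.

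**SAP Sections 1, 2.1 and 4.7.** The SAP takes precedence over other documents on the safety analyses, safety is its sole objective, and the final analysis is limited to safety.

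**The concern.** Once the study was stopped and efficacy dropped, the safety tables became the whole of the planned analysis. A protocol safety endpoint missing from the SAP therefore has nowhere else to be reported. Because the SAP gives itself precedence, a reader cannot assume that the protocol's list still applies where the SAP is silent.

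If the SAP is followed as written, vital signs required at three time points would go unreported. The study report would also lack a line answering the synopsis item on severe dysuria and hematuria. The change list gives no sign that either was removed, so a reader cannot tell a decision from an oversight.

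**Working it through.** The plan states no figure on this point and no arithmetic beyond counting applies. The check sets the three endpoint lists beside the SAP's planned outputs.

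| Item | Protocol synopsis | Protocol 8.6.1 | SAP 3.4.2 | Planned output in SAP Section 7 |
|---|---|---|---|---|
| All AEs | yes | yes | narrowed to TEAEs | tables and listing |
| Related AEs | yes | yes | yes | tables |
| SAEs | yes | yes | yes | overall table and listing |
| AEs leading to discontinuation | yes | yes | yes (TEAEs) | overall table and listing |
| AESI: dysuria, hematuria, grade 3 or higher | **yes** | **no** | **no** | **no named row** |
| Vital signs | **yes** | **yes** | **no** | **none** |
| Laboratory parameters (same protocol bullet as vital signs) | yes | yes | yes | listing |
| Deaths | yes | yes | yes | TEAEs leading to death: overall table and listing |

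**Count.** Of the seven synopsis bullets, 5 carry over in whole or reworded (AEs, related AEs, SAEs, discontinuation, deaths), 1 is halved (vital signs removed, laboratory kept) and 1 is absent (AESI): 5 + 1 + 1 = 7. Of the five declared changes, none covers the halved or the absent bullet.

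**What survives for vital signs.** No section of the SAP plans a table or listing. A clinically important abnormality could still surface if recorded as an AE, but the measurements themselves would not be reported.

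**What survives for AESI.** Section 7.3.1 gives patient counts by arm for each preferred term at Grade 3 or 4, so severe dysuria and severe hematuria can each be read off as a row. Three differences from the synopsis item remain:

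- The high-grade column stops at Grade 4, while the synopsis item is open-ended. The difference is Grade 5 events only, and the worst-grade summary and the listing of TEAEs leading to death could show those.
- Nothing identifies these rows as a protocol endpoint.
- The rows follow the TEAE definition, which ends 35 days after dosing. Protocol Section 5.4.10 records all AEs in Target patients to the 3-month visit.

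**The case against.** Much can be said for the SAP.

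- **On AESI it matches the protocol body.** Section 8.6.1 already lacks the item, so the inconsistency begins between the synopsis and that section. This stands, and it makes AESI the weaker half of the point. It does not apply to vital signs, which are in both protocol lists.
- **The change list claims only to be a list of important changes.** This is true. But in a SAP whose sole objective is safety, losing safety endpoints is important enough to be on it.
- **Protocol Section 8.6 describes no vital signs analysis.** Also true: it sets out methods for AEs, deaths, SAEs and laboratory results only. The form of any table is therefore open, and a listing would be a defensible minimum.

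A reader might also infer more than the documents support:

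- *That a composite of severe local bladder toxicity was pre-specified.* The synopsis names two events. It sets no at-least-one rule and does not include urinary tract hemorrhage.
- *That bleeding events are scattered over preferred terms and so hidden.* Section 1.3.2 lists "dysuria, hematuria and hemorrhage urinary tract, chemical cystitis, pollakiuria" for four patients given multiple instillations. The natural reading is that one patient had both hematuria and hemorrhage, and that patient would already be in the hematuria row. Section 7.3.1 of the SAP also counts each patient once per SOC.
- *That AESI was the trial's test of the higher dose.* The dose is twice that of the earlier Phase 3 studies (8 mg against 4 mg), and the concentration is 1.6 times as high (8/50 = 0.16 against 4/40 = 0.10 mg/mL). But no passage ties AESI to dose. Section 1.4 assigns the check on 8 mg/50 mL to IDMC review of the first 30 patients, and reports no clinically relevant safety concern with 8 mg in 40 mL (0.2 mg/mL).

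**Conclusion.** The point holds as a reporting gap and a contradiction between protocol and SAP. It is not evidence of harm or of concealed toxicity.

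The firm part is vital signs. They are an endpoint in both protocol lists, are collected at Screening, at the Treatment Visit and at Safety Follow-up/Month 3, and are absent from every planned output with no equivalent substitute.

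The lesser part is AESI. It is a synopsis endpoint that Section 8.6.1 and the SAP both lack. Grade 3 or 4 dysuria and hematuria stay visible by arm, so the loss is the named endpoint rather than the data.

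The size is one and a half of seven synopsis bullets, with neither loss declared. No numerical effect on results can be given, because the documents do not state how many patients were treated. The conclusion assumes that the SAP's own list and Section 7 are its full set of planned outputs. The correction is cheap and should be made.

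**What to change.** 1. **Vital signs.** Add them to SAP Section 3.4.2, and add to Section 7 a summary by actual treatment arm, or at least a listing as Section 7.4 gives laboratory results. SAP Section 4.4 already defines baseline if change is wanted.
2. **AESI.** Add to Sections 3.4.2 and 7.3.4, by actual arm, the number of patients with grade 3 or higher dysuria and the number with grade 3 or higher hematuria, optionally with the number having either. Define the rows as Grade 3 or higher, not Grade 3 or 4, state the time window, and supply a listing.
3. **Protocol.** Reconcile the synopsis with Section 8.6.1 on AESI.
4. **Summary of changes.** If either removal is intended, declare it there and give the reason.

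Any wider grouping of preferred terms, or a composite, would be an addition to the plan. It should be labelled post hoc if it is set after unblinding; the documents do not say whether unblinding has occurred.

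The cost is some SAP wording, one or two extra table rows, one short table and a listing, all from data the protocol already requires.
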